# **PROTOCOL SUMMARY**

ITEM	DESCRIPTION		
Title	GYROS: Gyrate Atrophy Ocular and Systemic Study		
Précis	GYROS: Gyrate Atrophy Ocular and Systemic Study Gyrate atrophy (GA) is a rare inherited chorioretinal degeneration that is associated with hyperornithinemia, an inborn error of metabolism caused by autosomal recessive mutations in the ornithine aminotransferase ( OAT ) gene. GA is characterized by childhood-onset nyctalopia and sharply demarcated areas of chorioretinal atrophy that initially involve the midperipheral fundus. The atrophic areas typically coalesce and enlarge towards the posterior pole in the second and third decades of life, leading to severe visual field constriction and vision loss if left untreated. The current standard care treatment of GA is an arginine restricted diet that is implemented in practice using dietary protein restriction with essential amino acid supplementation. However, dietary treatment is highly burdensome on patients and negatively impacts quality of life such that only about ~20% of patients can comply. Strict adherence to dietary protein restriction (particularly through adolescence), essential amino acid supplementation, and nutritional management of body weight especially during intercurrent illness and pregnancy are among the challenges of treatment. Periods of suboptimal dietary control led to plasma ornithine elevation and progressive chorioretinal degeneration. To facilitate a future interventional gene therapy clinical trial, there is a need to evaluate natural history of and the relationship between potential clinical trial outcome measures.		

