# FOOD RECORD AND SAMPLE COLLECTION SCHEDULE FOR ALL VISION COHORTS

	Screening	Baseline	4 M	8M	12M	16M	20M	24M	28M	32M	36M	40M	44M	48M
Clinical site coordinator contacts participant a		Х	Х	Х	Х	X	Х	Х	Х	Х	Х	Х	Х	Х
Three-day food record a		Х	Хb	X b	X b	X b	X b	X b	X b	Хb	X b	X b	X b	Х
Target Windows for Sample Collection			Wk 17 ± 4	$\begin{array}{c} Wk\\ 34\pm4 \end{array}$	Wk 52 ± 4	$\begin{array}{c}Wk\\69\pm4\end{array}$	$\frac{Wk}{86\pm4}$	$\begin{array}{c} Wk\\ 104\pm4 \end{array}$	Wk 121 ± 4	$\begin{array}{c} Wk\\ 138\pm4 \end{array}$	Wk 156 ± 4	Wk 173 ± 4	$\begin{array}{c} Wk\\ 190\pm4 \end{array}$	$\frac{Wk}{208\pm4}$
Fasting plasma amino acids c	Х	X (2)			Х			Х			Х			Х
Fasting blood spot amino acids d		Х	$\mathbf{X}^{\mathrm{d}}$	X d	Х	Xd	X d	Х	X d	X d	Х	X d	X d	Х
Request Albumin Lab Records e		Х			Х			Х			Х			Х
Body Weight		Х			Х			Х			Х			Х
Height f		Х			Х			Х			Х			Х

a. The Pre-Sample Participant Telephone Contact should occur four (4) – ten (10) days prior to scheduled sample collection date.
 Food record should occur for three (3) days leading up to the sample collection date. For at-home samples, the Post-Sample Collection Telephone Call should be completed within one (1) day after the scheduled sample collection date.

**b.** The Food Record is only collected if the participant is on an arginine-restricted diet. If the participant is not following an arginine-restricted diet, then the food record will not be recorded and collected. See Section 4.3 Food Record and Blood Sample Collection for more details.

c. Baseline only: two (2) fasting plasma samples collected on two (2) different days, within ten (10) days of Baseline Visit date.

d. Participant and/or caretaker administered remotely. Samples will be collected on all participants.

e. Request the most recent albumin records from the participant's overseeing physician. The albumin labs will be requested only if the participant is on an arginine-restricted diet.

f. Height will be measured annually in participants less than twenty-one (21) years of age at enrollment, otherwise height will only be collected at the Baseline Visit.

#### 1

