### 650 **4.2 Target Timelines**

- Target dates and windows for each study Follow-up Visit for all vision cohorts are shown below.
- Dates and windows are timed from Baseline Visit Date. Visits will be scheduled in the target window.

### 654

Table 4-1. Schedule for Follow-up Visits

VISIT SCHEDULE	TARGET DATE	TARGET WINDOW (AROUND TARGET DATE)
12 Month Visit	52 Weeks	± 4 Weeks
24 Month Visit	104 Weeks	± 4 Weeks
36 Month Visit	156 Weeks	± 4 Weeks
48 Month Visit	208 Weeks	$\pm 4$ Weeks

655 656

Table 4-2. Schedule for Remote Blood Spot Collection

BLOOD SPOT SCHEDULE	TARGET DATE	TARGET WINDOW (AROUND TARGET DATE)
4 Months	17 Weeks	± 4 Weeks
8 Months	34 Weeks	± 4 Weeks
16 Months	69 Weeks	± 4 Weeks
20 Months	86 Weeks	$\pm 4$ Weeks
28 Months	121 Weeks	± 4 Weeks
32 Months	138 Weeks	$\pm 4$ Weeks
40 Months	173 Weeks	± 4 Weeks
44 Months	190 Weeks	$\pm$ 4 Weeks

The goal will be for all participants to complete all scheduled visits. However, participants who,

because of unforeseen circumstances, are unable or unwilling to return for all follow-up visits

659 will be permitted to return for key visits only as an alternative to withdrawal from the study.

660 Additional office visits may occur as needed.

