701 702	
 
The Clinical Site Coordinator will transcribe the data from the food record on the FFB Study Website.
 

703 704 705	
 
A Central Dietitian Reviewer (CDR) will review food record on FFB Study Website to determine nutritional content. This information will be entered into the FFB Study Website.
 

706	(3) Sample Collection
707 708 709 710	
 
At the annual Follow-up Visits, the Clinical Site Personnel will collect one         
 
(1) fasting plasma sample on all participants and ship to KKI. The sample collection procedures are detailed in the GYROS Clinical Site Manual of Procedures.
 
 
 

711 712 713 714	At the annual Follow-up Visits, the Clinical Site Personnel will collect one (1) fasting blood spot fingerstick on all participants and ship to KKI. The sample collection procedures are detailed in the GYROS Clinical Site Manual of Procedures.
715 716 717	
 
At the annual Follow-up Visits, the Clinical Site Coordinator would request the most recent lab records with an albumin result if the participant indicated they are currently on an arginine-restricted diet.
 

 
718
 
719
 
720
 
721
 
722
 
723
 
	
 
Every four (4) months between annual Follow-up Visits, one (1) fasting blood spot fingerstick will be collected on all participants. The participant or caretaker will collect the sample and ship to the central laboratory, KKI. The blood spot collection kits and instructions will be provided. The sample collection procedures are detailed in the GYROS Clinical Site Manual of Procedures.
 

724	4.4 Follow-up Procedures
725 726 727 728 729	The following procedures will be performed at the Follow-Up Visits, unless otherwise specified. The testing procedures are detailed in the GYROS Clinical Site Manual of Procedures. An overview of the equipment and certification requirements for all testing is in Chapter 5.1: Study Procedure Requirements . All ocular testing will be performed in each eye, OD first and then OS. Follow-up visit procedures will last approximately seven (7) – eight (8) hours.
730	4.4.1 Follow-up Data Collection and Testing Cohorts 1 & 2
731	1. Medical updates to include:
732	• New or changed adverse events (AEs)
733	
 
New ocular procedures
 

734	
 
New or changed medications
 

735	• Request medical records and laboratory records if applicable.

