1188	mitigate the impact of missing data, specifically, mixed effects
1189	regression models and multiple imputation for the outcome values for
1190	all missing time points.
1191	
1192	(b) Characterize the natural history of ornithine levels associated with disease-
1193	causing OAT variants in the presence of standard care dietary treatment
1194	regimens over four (4) years.
1195	
1196	i. Longitudinal annual measures of ornithine will be explored by
1197	graphing the values for everyone ("spaghetti" plots) and analyzed to
1198	detect any linear trend in time with mixed effects models.
1190	detect any mical field in time with mixed effects models.
1200	(c) Determine within-patient variability of ornithine levels associated with
1200	disease-causing OAT variants in the presence of standard care dietary
1201	treatment regimens over four (4) years.
1202	
1203	i. The within-person standard deviation of ornithine levels will be
1204	estimated for the group of patients using a mixed effects model.
1205	Models will be based on levels from blood dot tests and from plasma
1206	testing over the four (4) years to determined long -term variability and
1207	on levels from blood dot tests over periods of six (6) months and of
1208	twelve (12) months to determine short-term variability. The coefficient
1209	of repeatability will be calculated to estimate the difference from
1210	baseline that would need to be exceeded to indicate that a treatment
1211	was causing an effect beyond random variability.
1212	2. Metabolic, Structure, and Function Relationships
1213	(a) Evaluate cross-sectional associations at baseline and each annual visit with
1214	scatterplots and Spearman correlation coefficients. Evaluate the association of
1215	changes in each outcome measure with changes the other outcome measures
1216	at each visit with scatter plots and Spearman correlation coefficients. Use
1217	mixed effects regression models to evaluate the association of change in each
1218	outcome measure with changes in each of the other outcome measures. With
1219	so many outcomes and only forty (40) patients, results will be interpreted
1220	cautiously because of both low powers to detect clinically meaningful
1221	associations and elevated Type I error rates due to multiple comparisons.
1222	3. Identify Rapid Progressors
1223	(a) The distribution of each outcome in terms of both absolute change and percent
1224	change from baseline to four (4) years will be summarized (including

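### Item 1(b)i confines the ornithine time course to annual values, so 8 of the 13 scheduled blood-spot values per participant stay out of it, although item 1(c) uses them for variability.

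*Protocol*

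**What the plan says.** The objective in Protocol section 8.3.1 is item "b) Characterize the natural history of ornithine levels associated with disease"-causing variants under standard dietary care over four years. Its analysis, item 1(b)i, is a single sentence. It opens "Longitudinal annual measures of ornithine will be explored by" plotting each person's values, and goes on to say that they will be analysed to "detect any linear trend in time with mixed effects models". The word annual governs both the plots and the model.

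The Protocol Summary lists two primary metabolic outcomes: plasma ornithine and blood-spot ornithine. In the Food Record and Sample Collection Schedule, the row "Fasting blood spot amino acids" is marked at Baseline and at every four-month column to 48M. Footnote d says of the samples between annual visits: "Participant and/or caretaker administered remotely. Samples will be collected on all participants". Section 4.3 agrees: between annual visits one fasting "blood spot fingerstick will be collected on all participants. The participant or caretaker will collect the sample and ship to the central laboratory". Section 4.2, "Table 4-2. Schedule for Remote Blood Spot Collection", lists the eight remote time points.

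Item 1(c), directly below 1(b), models blood-spot and plasma levels over four years, and blood-spot levels over 6- and 12-month periods. Its products are a within-person standard deviation for the group and a coefficient of repeatability. Section 1.5.3 says the study will determine whether the spot method is comparable to plasma.

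**The concern.** The plan collects a primary outcome every four months and then describes its course over time from the annual values alone. The Protocol Summary gives a reason to look between visits: "Periods of suboptimal dietary control led to plasma ornithine elevation and progressive chorioretinal degeneration". A rise that lasts a few months and settles before the next annual visit leaves no trace in annual values. Item 1(c) would register it only as a contribution to a pooled variance, which cannot show in whom, when or for how long ornithine was raised. The slope in 1(b) would also be estimated less precisely than the scheduled data allow. Both matter because the study is meant to inform the design of a later treatment trial.

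**Working it through.** **Count.** Blood spots are scheduled at months 0, 4, 8, …, 48, which is 1 + 12 = 13. Annual points are months 0, 12, 24, 36 and 48, which is 5. The remainder is 13 − 5 = 8 (62%), at months 4, 8, 16, 20, 28, 32, 40 and 44. This matches Table 4-2 exactly.

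**Slope precision, independent residuals.** Let Sxx be the sum of squared deviations of sampling time (years) from its mean, at the target weeks in the schedule.

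- Annual (weeks 0, 52, 104, 156, 208): Sxx = 10.0.
- Four-monthly (weeks 0, 17, 34, 52, …, 208): Sxx = 20.2.

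If only residual noise counts, the standard error (SE) ratio is √(10.0/20.2) = 0.70. True slopes also differ between people. With a between-person slope SD of τ residual SDs per year, the ratio for the mean slope is √[(τ² + 1/20.2)/(τ² + 1/10.0)]. The protocol gives no τ; 0.1 to 0.3 is assumed.

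- τ = 0.1: √(0.0595/0.1100) = 0.74, a fall of 26%.
- τ = 0.2: √(0.0895/0.1400) = 0.80, a fall of 20%.
- τ = 0.3: √(0.1395/0.1900) = 0.86, a fall of 14%.

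**Slope precision, serially correlated residuals.** Lapses lasting months imply that neighbouring four-monthly values are correlated. Take residual correlation exp(−gap/c), with c = 3 or 6 months (assumed), applied either to all of the residual variance or to half of it, the rest being independent noise. V is the generalised-least-squares variance of one person's slope, in units of the residual variance. The ratio is √[(τ² + V for 13 points)/(τ² + V for 5 points)].

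| Correlated share | c (months) | V, 5 points | V, 13 points | SE ratio, τ = 0.1 to 0.3 |
|---|---|---|---|---|
| All | 3 | 0.1014 | 0.0723 | 0.86 to 0.92 |
| All | 6 | 0.1096 | 0.0986 | 0.95 to 0.97 |
| Half | 3 | 0.1007 | 0.0613 | 0.80 to 0.89 |
| Half | 6 | 0.1050 | 0.0762 | 0.87 to 0.92 |

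The gain is therefore about 3% to 20%.

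**Chance of sampling a lapse.** Take one lapse of d months lying wholly within the 48 months, with a uniformly random start. For d no longer than the sampling interval, the chance that a sample falls inside it is (number of interior sampling points × d)/(48 − d). There are 3 interior annual points and 11 interior four-monthly points. Lapse lengths are assumed.

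- d = 3: annual 9/45 = 20%; four-monthly 33/45 = 73%.
- d = 4: annual 12/44 = 27%; four-monthly 44/44 = 100%.
- d = 6: annual 18/42 = 43%; every lapse of 4 months or longer is met by four-monthly sampling.

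**The case against.** The strongest reply is that the plan divides the work sensibly: trend to 1(b), fluctuation to 1(c). A reader might infer that the eight values go unused in the study. The text does not support that, because 1(c) draws on them. What 1(c) does not supply is a time course.

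Second, annual may simply describe plasma, which after Baseline is scheduled only once a year, and caution is reasonable while the spot method is still being compared with plasma. That caution is a good reason to keep the two sample types apart. It does not rescue the wording: read as plasma only, 1(b) would give blood-spot ornithine, a primary outcome, no time-course analysis at all.

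Third, section 8.1 calls the chapter a synopsis and framework, and an analysis plan not shown here may add detail. But the sentence is not silent on which values to use. It names them, and a later plan that follows it inherits the limit.

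Fourth, lapses leave other traces. Participants on the restricted diet keep food records every four months, and adherence is a listed risk factor. This softens the consequence, but it does not show the ornithine course itself.

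Two numerical readings also go too far. A fall of 14% to 26% in the standard error depends on independent residuals, which sits badly with lapses lasting months. Chances of 25% and 75% (3/12 and 3/4) for a 3-month lapse ignore the ends of the study.

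**Conclusion.** The point holds for item 1(b): as written, it leaves 8 of 13 scheduled values of a primary outcome out of the only analysis of the ornithine time course. It is a stated restriction that should be changed, not an error in any of the protocol's figures, and no data are lost to the study as a whole. The larger cost is in what can be seen: about 20% against 73% for an assumed 3-month lapse, with annual sampling below 50% for lapses of up to 6 months. The precision cost is smaller and less certain: about 14% to 26% on the SE of the mean slope with independent residuals, and about 3% to 20% with correlation over 3 to 6 months. These ranges rest on an assumed between-person slope SD of 0.1 to 0.3 residual SDs per year, on assumed correlation and lapse lengths, and on complete sampling at the target weeks. It would also be too strong to say that 1(b) consists of one linear trend, since individual plots are planned too; they are limited to the same annual values.

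**What to change.** In section 8.3.1, item 1(b)i, replace the reference to annual measures with wording such as: All scheduled blood-spot ornithine values (Baseline and every four months to 48 months) will be plotted for each participant and modelled on actual sampling date. Plasma values (Baseline and annual) will be plotted and modelled as a separate series. The blood-spot model will include a term for home or site collection and will allow for serial correlation. The annual-only model can stay as a secondary analysis if wanted.

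The series should stay separate because comparability of spots with plasma is still to be determined. The change needs no new samples, visits or participants, since the spots are already scheduled for everyone. The downside is that home-collected spots may be noisier; the home/site term deals with a systematic shift, and the annual-only model gives a check.

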Impact	
 
disease-causing OAT variants.
 
The expected impact of the OAT gene natural history study is to inform a future interventional clinical trial design and implementation, including the following: 
 
Determine within-patient variability of ornithine levels.
 
Develop quantitative measures of progression of the area of preserved retina and establish its reproducibility, sensitivity to change, and relationship with other measures.
 
Establish rates of progression of retinal degeneration on all functional, structural, and patient-reported outcome measures, and determine which measures are most sensitive to change.
 
Determine primary time points and duration for a planned future treatment trial.
 
Use variability and inter-eye correlation of outcomes for trial sample size calculations.
 
Identify candidates for the future trial, including eligibility criteria based on risk factors and cut points for severity of disease most likely to benefit from treatment.
 
 
 
			
Study Design Number of Sites	Multicenter, longitudinal, pro assigned to one (1) of three (2 kinetic visual fields (VF). Approximately 12			
	Structural Outcomes:	1		
	Key Assessments	Test	Equipment	Reading Center
Outcomes	Primary: Quantitative measures of progression of the area of preserved retina and of the area of lesions in standardized regions*	Fundus autofluorescence (FAF)	Optos	Yes
	Primary: Use with FAF for assessments noted above	Ultra-Widefield Color Photography	Optos	Yes
	Ellipsoid zone (EZ) area	Spectral domain optical coherence tomography (SD-OCT)	Heidelberg Spectralis	Yes
	Presence and type of cataract (posterior subcapsular and cortical cataract) **	Red reflex photography	Digital camera capable of capturing external eye photos Megapixels of >=3MP Magnification of 30-40 degrees Digital camera export in PNG, TIF, DICOM or BMP	Yes

ITEM	DESCRIPTION			
	Foveal avascular zone (FAZ) area and macular vessel density	OCTA Ancillary test at subse sites	list	Yes
	*Other approaches to grading m **Ocular exam by investigator v cataract. Functional Outcomes:			uclear sclerosis
	Key Assessments	Test	Equipment	Reading Center
	Visual field sensitivity measured with quantitative topographic analysis (Hill of Vision)	Static Perimetry	Octopus 900 Pro	Yes

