#### 167 **1.4 Study Objective**

- 168 **Natural History** Characterize the natural history of ornithine levels and retinal degeneration
- 169 (RD) associated with disease-causing *OAT* variants in the presence of standard care dietary
- 170 treatment regimens over 4 years.
- 171 **Metabolic-Structure-Function Relationships** Explore the relationships between structural 172 and functional RD outcome measures and plasma ornithine levels.
- 173 Identify Rapid Progressors Explore the relationship of possible risk factors (genotype,
- phenotype, environmental, comorbidities, and standard care dietary regimen) with severity and
- 175 progression of metabolic, functional, structural, and patient-reported outcomes.

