### 1150 8.3.1 Primary Objective Analysis

1151 The primary objectives of the natural history study and brief analysis plan for each are as 1152 follows.

**1.** Natural History 1153 (a) Characterize the natural history of retinal degeneration associated with 1154 disease-causing OAT variants over four (4) years, as measured using 1155 functional, structural, and patient-reported outcome measures. 1156 1157 i. Functional and structural measures: The distribution of each 1158 outcome at each visit will be summarized (including tabulating 1159 categorically, as well as means, SDs, medians, quartiles, ranges; both 1160 the absolute change and percent change will be evaluated, tests 1161 performed multiple times per visit will be analyzed using the average 1162 of all available tests). To determine the average annual rate of 1163 progression in the population for each outcome, a mixed effects model 1164 will be fit using all available outcome data at baseline and all annual 1165 visits. Both the correlation in outcomes over time and the correlation 1166 in outcomes between eyes will be accommodated by the model. 1167 Mixed models adequately accommodate missing values when missing 1168 values are missing at random (MAR). A second method of 1169 accommodating missing values will be through multiple imputation for 1170 the outcome values for all missing time points (including participants 1171 who discontinue follow up prior to forty-eight (48) months). 1172 Secondary analyses using binary definitions of outcome measures will 1173 also be explored in time to event analyses; Kaplan-Meier estimates 1174 with 95% confidence intervals will be calculated. 1175 1176 **PRO measures:** The scoring of each questionnaire will be completed ii. 1177 according to the procedures recommended by the developers of the 1178 questionnaire for each instrument. Baseline scores will be cross 1179 tabulated with categorical (severity of disease) versions of the outcome 1180 measures of interest at baseline. Changes in scores will be cross 1181 tabulated with binary (progression of disease) versions of the outcome 1182 measures of interest at the 24- and 48-month visits. A generalized 1183 linear model adjusted for baseline differences will be explored. 1184

1185	Partially completed questionnaires will be managed using methods
1186	recommended by the developers of the specific questionnaire. When
1187	no questionnaire is completed, we will use statistical methods that

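### One group-wide ornithine repeatability limit, read as the mark of a treatment effect beyond random variability, can be too large for diet-controlled patients

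*Protocol*

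**What the plan says.** Protocol section 8.3.1, item 1(c)i, has the within-person SD of ornithine levels "estimated for the group of patients using a mixed effects model". Separate models are planned: blood spot over 4 years, plasma over 4 years, and blood spot over 6 and 12 months for short-term variability. A coefficient of repeatability follows, described as estimating the difference from "baseline that would need to be exceeded to indicate that a treatment" "was causing an effect beyond random variability". The item names no relative scale, diet stratum or diet term.

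Other sections bear on this:

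- The Impact row of the Protocol Summary lists first: "Determine within-patient variability of ornithine levels".
- Section 1.2.1 gives levels below 200 µM on the arginine-restricted diet. Section 1.1 gives about 15 times normal on an unrestricted diet.
- The Précis says: "Periods of suboptimal dietary control led to plasma ornithine elevation". Section 4.3 provides for participants who start or stop the diet during the study.
- Section 1.4 will explore risk factors ("phenotype, environmental, comorbidities, and standard care dietary regimen) with severity and" "progression of metabolic, functional, structural, and patient-reported outcomes").
- For functional and structural measures, item 1(a)i states that both "the absolute change and percent change will be evaluated, tests" being averaged where repeated. Item 3(a) also summarises each outcome as absolute and percent change, stratified by risk factors that include baseline ornithine and diet adherence.

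**The concern.** The protocol describes widely separated ornithine levels and names diet as a cause of movement between them. A single SD pooled over such a group is dominated by the patients with the larger SD. If those are the patients with high levels, the limit is set by them and then applied to diet-controlled patients, for whom a real fall could look like noise. A participant who starts or stops the diet adds a step change to the pooled SD, and item 1(c)i then calls that explained step random.

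Estimating total variability under standard care is not at fault, because that is what objective 1c asks for. The difficulty lies in reading that quantity as a random-noise limit for a treatment effect. A future trial could inherit the limit as a yardstick.

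**Working it through.** The protocol states no ornithine SD, CV, coefficient or switching rate, so there is no figure of its own to reproduce.

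**Inputs.** From the protocol: on-diet level 200 µmol/L (upper edge of the range in section 1.2.1); share on diet 20% (the general compliance figure in the Précis, used as a stand-in for enrolment); 40 participants in Vision Cohorts 1 and 2; 13 blood spots per participant over 4 years. Assumed: off-diet mean L = 300 (low end), 600 or 800 µmol/L; within-person CV 10 to 30%; switching shares up to 20%.

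**Step 1: a bound that needs no CV.** The coefficient is K × SD with K = 1.96 × √2 = 2.77. It passes 200 µmol/L once SD exceeds 200 / 2.77 ≈ 72 µmol/L. Above that, no fall from a baseline of 200 can exceed the limit.

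**Step 2: pooled limit against each group's own limit, no switching.** With SD proportional to level to the power b, pooled over on-diet = √(0.2 + 0.8 × (L/200)^(2b)). The off-diet row divides the b = 1 ratio by L/200.

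| | L = 300 | L = 600 | L = 800 |
|---|---|---|---|
| On diet, constant CV (b = 1) | √2.0 = 1.4 | √7.4 = 2.7 | √13.0 = 3.6 |
| On diet, square root (b = 0.5) | √1.4 = 1.2 | √2.6 = 1.6 | √3.4 = 1.8 |
| On diet, constant SD (b = 0) | 1.0 | 1.0 | 1.0 |
| Off diet, constant CV | 0.94 | 0.91 | 0.90 |

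Under constant CV the pooled limit is K × CV × 200 × ratio: 78/151/200 µmol/L at CV 10% and 157/302/400 at CV 20%. It reaches 200 µmol/L at a CV of 25.5/13.3/10.0%.

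**Step 3: diet switching.** This was simulated with 40 participants, lognormal errors and one switch at a random spot. The 4-year model took the residual SD after person effects and linear time; the 12-month model pooled the SD within 12-month intervals. No diet handling was applied in this table.

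| L = 600, CV 10% | Blood spot limit, µmol/L |
|---|---|
| No switching | about 150 |
| 20% switch, 12-month model | about 186 |
| 20% switch, 4-year model | about 258 |

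The effect shrinks as CV rises or switching becomes rarer. With 2.5% switching at L = 600, the 4-year limit goes from 151 to 169 at CV 10% and from 302 to 310 at CV 20%.

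**Step 4: a relative limit.** On the log scale, with s = √ln(1 + CV²), the limit for a fall is 1 − exp(−K × s): 24/42/56% at CV 10/20/30%. It scales with each patient's baseline.

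**Step 5: what the narrower limit costs.** An untreated participant who starts the diet exceeds it with probability 1 − Φ((K × s − ln(L/200)) / (√2 × s)). For L = 300 and 600 respectively, this is 82% and over 99% at CV 10%, 30% and 98% at CV 20%, and 16% and 75% at CV 30%.

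**The case against.** The strongest reply is that Chapter 8 calls itself a synopsis and framework, and that scale, covariates and strata usually belong in the SAP. Item 1(c)i never uses the word absolute, and a back-transformed log coefficient could still be called a difference from baseline. Part of this stands: absolute is an inference from an SD of levels and a difference from baseline. But the protocol itself fixes the group-level SD and the meaning given to its coefficient, and that meaning is what can mislead.

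A reader might infer more than the documents support:

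- *That the limit is wrong.* It is not shown to be. With SD constant across levels and nobody switching, one limit is valid. For off-diet patients it is nearly right even under constant CV.
- *That diet changes spoil every planned coefficient.* The 12-month spot model already removes most of the inflation, and a 6-month model is planned as well.
- *That the protocol confines ornithine to absolute differences or ignores diet.* Item 3(a) covers percent change and diet adherence for each outcome. It does not, however, supply a percent repeatability limit.
- *That diet variation should be taken out of objective 1c.* The objective is variability under standard care, so total variability is a legitimate result.
- *That the food-record rule identifies diet changes.* Under section 4.3 a participant who stops the diet continues the record, so a stop leaves no trace there.

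It is also true that a later trial could recompute the limit from archived data.

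**Conclusion.** The point holds as a conditional one. Item 1(c)i can yield a limit that is too large for diet-controlled patients, and it labels as random some variation that the protocol elsewhere attributes to diet. The size cannot be determined from the protocol. It ranges from no error to a factor of 3.6, depending on how SD changes with level, on off-diet levels of 300 to 800 µmol/L, and on 20% of participants being on diet at 200. The switching effect depends on an assumed switching rate and falls mainly on the 4-year models. Nothing decided within GYROS changes. A correction is still worth making, because the variability estimate heads the list of outputs for the future trial and the change is cheap.

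**What to change.** In section 8.3.1, item 1(c)i:

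1. Keep the overall within-person SD and its coefficient as the objective 1c result. Describe them as within-person variability under standard care, diet changes included, and not as random variability.
2. Add a coefficient of repeatability on log ornithine, reported as a percent change, overall and by diet status. Take diet status from the annual visits, where section 4.3 already asks whether the participant is currently on the diet, and not from the food-record rule. For blood spots, use 12-month intervals with the same diet status at both bounding visits. For plasma, fit current diet status as a time-varying term.
3. State that the added limit applies only while diet is stable.

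Cost: analysis wording and slightly more analysis, with no new samples. If 10 to 20% of 40 participants switch once, about 4 to 8 of 40 × 4 = 160 intervals drop out, provided the switch shows at the bounding visits. On/off status misses graded lapses and changes that reverse between visits. The on-diet estimate is imprecise. With 20% of 40 = 8 participants, the 95% interval for the SD is about 0.85 to 1.21 times its value for spots (8 × 4 × 2 = 64 df) and 0.82 to 1.28 for plasma (8 × 5 = 40 df, screening sample left out), from √(df/χ²). The narrower limit can also be exceeded by an untreated participant who starts the diet, which is why the third change is needed.
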